Study Protocol

Preoperative Psychotherapy and Its Effects on Anxiety, Hemodynamics, and Pain in Living Kidney Donors (PREPSY-KD)

Protocol Version: 1.0

Protocol Date: November 2023

Organization's Protocol ID: KAEK-840

1. Background and Rationale

Living kidney donation is an essential treatment modality for end-stage renal disease (ESRD). Donor nephrectomy, while performed in healthy individuals, is associated with significant psychological stress due to hospitalization, surgical anticipation, anesthesia concerns, and uncertainty regarding recovery. Preoperative anxiety has been shown to negatively affect postoperative pain, hemodynamic stability, anesthetic requirements, and overall recovery.

Psychotherapeutic interventions such as psychoeducation, guided imagery, and diaphragmatic breathing exercises have demonstrated benefits in reducing perioperative anxiety and improving physiological parameters. However, there is limited prospective evidence evaluating the effect of structured preoperative psychiatric consultations on anxiety, hemodynamic responses, and postoperative pain in living kidney donors.

This study aims to assess whether a brief standardized psychiatric consultation administered before donor nephrectomy affects perioperative anxiety levels, intraoperative hemodynamics, and postoperative pain outcomes.

2. Study Objectives

Primary Objective

- To evaluate the effect of preoperative psychiatric consultation on postoperative pain scores measured via the Visual Analog Scale (VAS) at predefined postoperative time points.

Secondary Objectives

- To compare preoperative and postoperative anxiety levels between intervention and control groups using the Beck Anxiety Inventory (BAI).
 - To compare intraoperative hemodynamic parameters (heart rate, systolic and diastolic blood pressure, SpO₂) between groups.
 - To evaluate postoperative oxygen saturation trends.
 - To assess postoperative opioid consumption and antiemetic requirements.
-

3. Study Design

- **Study Type:** Interventional

- **Design:** Prospective, randomized, parallel-assignment clinical trial
- **Number of Arms:** 2 (Intervention vs. Standard Care)
- **Masking:** Single-blind (Outcomes Assessor)
- **Allocation:** Randomized
- **Primary Purpose:** Supportive Care
- **Study Duration:** November 2023 – November 2024

Randomization was performed via sealed envelopes during preoperative evaluation. Outcome assessors evaluating VAS scores were blinded to group allocation.

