4. Study Population

Inclusion Criteria

- Age \geq 18 years
- ASA physical status I-II
- Voluntary participation with signed informed consent
- Living kidney donor scheduled for elective donor nephrectomy

Exclusion Criteria

- Diabetes mellitus diagnosis
 - Development of postoperative delirium
 - Known psychiatric illness or psychiatric medication use
 - Neurological or musculoskeletal disorders
 - Chronic pain or chronic pain treatment
 - Recent significant psychological trauma
 - Analgesic drug use within the last month
-

5. Interventions

Intervention Group: Preoperative Psychiatric Consultation

Participants received a standardized 15-minute psychiatric session one hour before surgery under psychiatrist supervision, including:

- History-taking (3–5 minutes)
- Psychoeducation regarding anxiety and surgical preparation (3–5 minutes)
- Diaphragmatic breathing exercises (1–3 minutes)
- Guided imagery techniques (3–5 minutes)

The intervention was delivered by an anesthesiologist trained by a psychiatrist through structured educational sessions.

Control Group: Standard Preoperative Care

Participants received routine preoperative evaluation. No psychiatric intervention was performed.

6. Outcome Measures

Primary Outcome

- Postoperative Pain Score (VAS 0–10)**

Time Frame: Postoperative 30 minutes, 2 hours, 6 hours, 12 hours, 24 hours, and 48 hours.

Secondary Outcomes

- State Anxiety Score (Beck Anxiety Inventory, 0–63)**

Time Frame: 30 minutes preoperatively, postoperative 24 hours, postoperative 48 hours.

- Postoperative SpO₂ Levels (%)**

Time Frame: Postoperative 30 minutes, 2 hours, 6 hours, 12 hours, 24 hours, 48 hours.

- Intraoperative Heart Rate (beats/min)**

Time Frame: Pre-induction, 30 minutes after induction, 1 hour after induction.

- Intraoperative SpO₂ Levels (%)**

Time Frame: Pre-induction, 30 minutes after induction, 1 hour after induction.

- Intraoperative Systolic Blood Pressure (mmHg)**

Time Frame: Pre-induction, 30 minutes after induction, 1 hour after induction.

- Intraoperative Diastolic Blood Pressure (mmHg)**

Time Frame: Pre-induction, 30 minutes after induction, 1 hour after induction.

- Total Opioid Consumption (mg)**

Time Frame: Intraoperative period and postoperative first 24 hours.

- Antiemetic Use (Yes/No, mg)**

Time Frame: Intraoperative period and postoperative first 6 hours.

7. Data Collection Procedures

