Data will be collected at standardized time points by trained staff members. Hemodynamic parameters will be retrieved from anesthesia monitoring records. Pain scores will be evaluated using a 10 cm Visual Analog Scale. Anxiety assessments will be performed by a blinded outcomes assessor.

8. Statistical Analysis Plan

- Categorical variables: χ^2 or Fisher's exact test
- Continuous variables with normal distribution: Independent samples t-test
- Non-normal distribution: Mann-Whitney U test
- Repeated measurements: Repeated Measures ANOVA or Friedman test
- Correlations: Pearson or Spearman coefficients
- Significance threshold: $p < 0.05$
- Software: SPSS 15.0 version

All analyses will be performed per-protocol.

9. Ethical Considerations

- Ethics Committee Approval: **Akdeniz University Clinical Research Ethics Committee**
Approval Number: **2023-KAEK-20 / 840**
- Board Status: Approved
- Participation is voluntary; written informed consent obtained from all donors.
- No investigational drug or device used.
- Risks are minimal and limited to standard perioperative care.

10. Study Timeline

- Start of enrollment: November 1, 2023
- Primary completion: October 1, 2024
- Study completion: November 1, 2024

11. Data Management and Monitoring

A formal Data Monitoring Committee is not required due to minimal-risk behavioral intervention and absence of investigational medicinal products.

All data will be anonymized and stored securely following institutional data protection guidelines.

12. Publication Plan

Findings will be submitted to peer-reviewed anesthesiology and transplant journals and may be presented at national and international conferences.

13. References

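### Per-protocol is the only analysis population, it is undefined, and postoperative delirium is an exclusion, so randomised donors can be dropped and no analysis of all randomised donors is planned

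*Combined protocol and SAP*

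**What the plan says.** Section 8 (Statistical Analysis Plan) closes its list of tests with one sentence on the population: "All analyses will be performed per-protocol". It gives no adherence criterion, no list of disqualifying deviations, no rule for missing data, and no statement of who decides on removal or when. The protocol mentions no analysis of all randomised donors, even as a sensitivity analysis.

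Four other sections bear on this:

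- Section 2, primary objective: "To evaluate the effect of preoperative psychiatric consultation on postoperative pain scores". No non-inferiority aim or margin is stated.
- Section 3: "Randomization was performed via sealed envelopes during preoperative evaluation".
- Section 4, among the exclusion criteria: "Development of postoperative delirium".
- Section 5, intervention arm: "Participants received a standardized 15-minute psychiatric session one hour before surgery under psychiatrist supervision". Control arm: "No psychiatric intervention was performed".

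The primary outcome in section 6 is VAS pain, with "Time Frame: Postoperative 30 minutes, 2 hours, 6 hours, 12 hours, 24 hours, and 48 hours".

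**The concern.** Randomisation makes the two arms comparable as allocated. A rule that selects donors on what happens after allocation gives that up. If the reason for removal is related to pain and acts differently in the two arms, the VAS comparison is biased, and so are the secondary comparisons that share the population.

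The plan leaves several routes to removal open. Delirium is written down and applies to both arms. Since the per-protocol set is undefined, section 5 suggests two more: a session not received or not completed, which can occur only in the intervention arm, and a psychiatric intervention received in the control arm. Section 1 itself says that preoperative anxiety worsens postoperative pain. If anxious donors were less likely to complete the session, which is a possibility and not a documented fact, removal would be linked to the primary outcome. An undefined set can also be settled after results have been seen.

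**Working it through.** **Order of events.** Allocation takes place at the preoperative evaluation (section 3), the session one hour before surgery (section 5), then surgery, then VAS from 30 minutes to 48 hours (section 6). Delirium after surgery can be observed only after the first three steps. A donor may already have VAS scores, and will have intraoperative data, when the exclusion is met. As written, sections 4 and 8 together allow that donor to be dropped.

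**Is there a stated reason for per-protocol?** None. The trial looks for an effect between two parallel arms, and no non-inferiority margin appears.

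**Size.** The documents give no sample size, SD, delirium rate or deviation rate, so there is no figure of the plan's own to reproduce. The following is illustration only.

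Assumed inputs: SD 2 VAS points; n = 30 or 50 randomised per arm; one VAS mean compared with a two-sided 5% test (the plan has six times and does not state sidedness); no true effect; 0–20% removed per arm; removed donors 0–2 points higher than retained donors.

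In arm k let p_k be the fraction removed and d_k the mean VAS of removed minus retained donors. The retained mean lies p_k·d_k below the mean of all randomised donors in that arm. Hence, with I the intervention and C the control arm:

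- Bias in favour of the intervention = p_I·d_I − p_C·d_C
- SE = 2·√[1/(n(1−p_I)) + 1/(n(1−p_C))]
- Type I error = P(|Z + bias/SE| > 1.96)

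Worked case, 20% removed from the intervention arm only, gap 2, n = 30: bias = 0.20 × 2 = 0.40; SE = 2·√(1/24 + 1/30) = 0.548; bias/SE = 0.73; type I error 11.3%. With n = 50, SE = 0.424 and type I error is 15.6%.

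| Removed, I / C | Gap, I / C | Bias | Type I error, n = 30 | n = 50 |
|---|---|---|---|---|
| 10% / 10% | 1.5 / 1.5 | 0 | 5.0% | 5.0% |
| 20% / 20% | 2 / 2 | 0 | 5.0% | 5.0% |
| 10% / 5% | 1.5 / 1.5 | 0.075 | 5.2% | 5.4% |
| 20% / 10% | 2 / 2 | 0.20 | 6.5% | 7.5% |
| 10% / 10% | 1.5 / 0 | 0.15 | 5.9% | 6.5% |
| 5% / 0 | 1 / – | 0.05 | 5.1% | 5.2% |
| 10% / 0 | 1.5 / – | 0.15 | 5.9% | 6.5% |
| 20% / 0 | 2 / – | 0.40 | 11.3% | 15.6% |
| 0 / 20% | – / 2 | −0.40 | 11.3% | 15.6% |

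A simulation with the t-test (40,000 trials per case) agrees: 20% / 20% with gap 2 gives 4.9% and 4.8%; 20% / 10% with gap 2 gives 6.2% and 7.5%; 20% / 0 with gap 2 gives 11.1% and 15.2%.

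These figures are not bounds. If removed donors had higher pain in one arm and lower in the other (20% per arm, gaps +2 and −2), the same formulas give bias 0.8 and type I error of 28% and 43%.

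**The case against.** The strongest reply is that little removal may occur. The intervention is a single 15-minute session shortly before surgery, so there is little time for non-adherence. Donors are ASA I–II, and known psychiatric illness and neurological disorders are excluded. With 5% removed from one arm and a 1-point gap, type I error is only 5.1–5.2%; the larger figures need 20% removal from one arm and a gap of one SD. This stands as a point about size: if few donors deviate, the two analyses nearly coincide. But the documents give no rate, and without an analysis of all randomised donors a reader cannot tell whether that is the case.

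Second, delirium is the only post-randomisation ground actually written down; the others are inferred from section 5. That is true, and it follows from the set being undefined.

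Third, a delirious donor may be unable to give a reliable VAS score. That justifies recording the affected scores as missing with a reason. It does not justify discarding the donor's earlier scores or intraoperative data.

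Fourth, an as-assigned analysis still lacks donors whose scores were never taken. This also stands: the change recovers recorded data and makes the remaining loss visible by arm, but it cannot restore unrecorded outcomes.

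**Conclusion.** The concern holds and must be fixed. That per-protocol is the sole population, that it is undefined, and that one exclusion can be met only after randomisation all rest on the text and need no assumption. Followed as written, the plan drops randomised donors because of later events in a trial meant to estimate an effect, and one sentence does so for the primary and every secondary outcome.

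The size is unknown. It is zero if removal is unrelated to pain, or equal in both arms with equal gaps. In the assumed cases tabulated above, bias runs from −0.4 to +0.4 VAS points, and type I error from 5.0% to 11.3% (30 per arm) or 15.6% (50 per arm); other inputs give other ranges. Nothing in the documents shows that any donor was in fact dropped, or which arm would gain.

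**What to change.** Replace the population sentence in section 8 with:

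> The primary analysis of each outcome includes all randomised donors with data for that outcome, in the arm assigned, whether or not the session was received or completed. For outcomes measured repeatedly, this applies at each time point. Donors without outcome data, and all post-randomisation exclusions, are reported by arm with reasons. A per-protocol analysis is a sensitivity analysis only; its set is defined for both arms before the data are analysed (eligibility met; intervention arm: session delivered as described in section 5; control arm: no psychiatric intervention received).

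Reconcile section 4 with this. For the analysis, postoperative delirium is a reported post-randomisation event and not a reason to drop a randomised donor; scores that could not be obtained are recorded as missing with the reason. This concerns the analysis population only and sets no clinical rule.

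The tests in section 8 can stay. For normally distributed data the plan has "Continuous variables with normal distribution: Independent samples t-test"; that test, or Mann-Whitney U, applied at each time uses every score available at that time. If VAS is instead analysed over all six times jointly, repeated measures ANOVA or Friedman would drop donors with partly missing scores; a mixed model for repeated measures would keep them, assuming data missing at random.

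The timeline in section 10 ends on November 1, 2024. If the data have already been analysed, label the change and the per-protocol definition as post hoc.

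The cost is wording, one reconciliation of the exclusion list and a little extra analysis, with no extra donors. The estimated effect may come out smaller or larger. The analysis is complete only if outcomes were recorded for donors who deviated or became delirious; otherwise the number missing is reported by arm.
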